1. BACKGRAUND FOR THE TRIAL

Pulmonary embolism (PE) is a complex clinical problem. The prevalence of PE is high and reaches 30-40 people per 100 000 populations in Russia [1]. PE is one of the leading causes of death, morbidity and hospitalization in Europe [2]. It has been shown that in six EU countries (population about 450 million people), the mortality rate from PE is higher than from AIDS, breast cancer, prostate cancer and road traffic accidents combined, and is 11% of the entire population surveyed [2].

In the Russian Federation, mortality from PE is very high and ranges from 10-30%, depending on modern diagnostics and the use of adequate methods of treatment, primarily thrombolytic therapy.

The indication for thrombolytic therapy is massive PE, defined by size scales and risk stratification. Massive PE is defined in the presence of signs of shock or hypotension, which corresponds to III-V class PESI [1].

In accordance with European [1] and Russian [2] Guidelines for massive PE treatment, the following thrombolytic drugs are used:

- 1) streptokinase according to the standard scheme of administration for 12-24 hours or accelerated scheme for 2 hours;
- 2) urokinase according to the standard (12-24 hours) or accelerated schemes for 2 hours;
- 3) alteplase according to the standard scheme of 100 mg for 2 hours.

The recently completed PEITHO study used the «gold standard» thrombolytic therapy for acute ST-segment elevation myocardial infarction (STEMI) tenecteplase in patients with intermediate-risk PE with signs of right ventricular (RV) disease according to a single bolus administration at a dose of 30-50 mg, depending on body weight. Tenecteplase was shown to be highly effective, combined with a large number (6.3%) of hemorrhagic stroke, which did not allow tenecteplase to be included in the list of recommended thrombolytics for PE [3].

FRIDOM 1 study showed equal efficacy and safety of Fortelyzin®, 15 mg as a single bolus, regardless of body weight, compared with Metalyse® (tenecteplase), administered as a single bolus of 30-50 mg depending on body weight, in patients with STEMI. This study demonstrated the high efficacy of Fortelyzin® and its safety, the absence of major bleeding and hemorrhagic stroke in patients with STEMI complicated by cardiogenic shock [5, 6].

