Fortelyzin®, given as a single bolus of 10 mg regardless of body weight, was non-inferior to Actilyse® (alteplase) bolus infusion at a dose of 0.9 mg/kg (maximum 90 mg) for patients with acute ischemic stroke within 4.5 hours of symptom onset in a recently completed FRIDA trial. Mortality, symptomatic intracranial hemorrhage, and serious adverse events did not differ significantly between groups [7].

These results were decisive for resolving the issue of the possibility of using Fortelyzin® in patients with massive PE accompanied by shock and hypotension, where thrombolytic therapy is the method of choice.

Taking together, the purpose of this trial is to evaluate the efficacy and safety of the Fortelyzin® with its single bolus administration in comparison with the bolus-infusion administration of the Actilyse® in patients with massive PE.

Rationale for the Fortelyzin® dose in patients with massive PE

The FRIDOM1 study Fortelyzin® was used as a single bolus injection of 15 mg in patients with STEMI, including patients with cardiogenic shock. Thrombolytic therapy with Fortelyzin® at a dose of 15 mg in these patients showed high efficacy and safety.

The proposed comparison drug Actilyse® is the «gold standard» in the massive PE treatment. It used at a dose of 100 mg, the same as for STEMI.

In this regard, the dose of Fortelyzin® should be identical to that used for STEMI, 15 mg administered as a single bolus.

Thus, Fortelyzin® in patients with massive PE can be considered justified in comparison with Actilyse® as the “gold standard” for PE thrombolytic therapy.

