The second mechanism of Forteplase® fibrin selectivity results from the difference in the inhibition rate of the plasmin-Forteplase® complex in the bloodstream and on the surface of fibrin, i.e. on the clot. This complex is neutralized by α_2 -antiplasmin in blood plasma 100 times faster than on the fibrin surface.

Fibrin selectivity of Fortelyzin® increases the therapeutic efficacy and prevents the activation of circulating plasminogen, and may also increase the safety of thrombolytic therapy by minimizing exposure to circulating blood fibrinogen.

The thrombolytic fibrin selectivity also causes its dose-dependent effect. The dose of the moderately selective thrombolytic – Actilyse® is 100 mg for STEMI patients and 90 mg for patients with ischemic stroke, while the dose of the fibrin-selective thrombolytic – Fortelyzin® – is 15 mg for STEMI and 10 mg for ischemic stroke.

Also, Fortelyzin® does not cause the formation of neutralizing anti-staphylokinase antibodies in the blood. In rare cases, the transient formation of anti-drug antibodies (in low titers) may be observed.

After intravenous administration of Fortelyzin®, there is a slight decrease in blood fibrinogen, less than 10 %, within 1 day after administration.

Fortelyzin® has a short half-life. The main organ for excretion of the drug (75%) is the liver.

Pharmacokinetics of a single bolus injection of Fortelyzin® at a dose of 15 mg for STEMI patients showed a short half-life ($t_{1/2\alpha}$) of 5.7 minutes and $t_{1/2\beta}$ in the so-called terminal phase of 30 minutes.

Pharmaceutical form: Lyophilizate for preparation of a solution for intravenous administration.

One vial of Fortelyzin® contains:

Active substance: Forteplase® (a recombinant protein containing the amino acid sequence of staphylokinase), 5 mg (745,000 IU).

Excipients: L-arginine – 15,0 mg, L-histidine – 2,0 mg, glycine – 30,0 mg, povidone -17 – 20,0 mg, polysorbate-20 – 0,4 mg.

Solvent: 5mL ampule of sodium chloride 0.9% solution for injection.

The results of Fortelyzin® preclinical studies

Preclinical study of toxicological properties was conducted in E.I. Chazov Russian Cardiology Research Complex of the Ministry of Health of the Russian Federation in accordance with the requirements set out in the “Manual on Experimental (Preclinical) Study of New Pharmacological Substances” (Moscow, 2005) of the Federal Service for Surveillance in Healthcare and Social Development of the Russian Federation.

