7.1. Inclusion criteria

- Men and women aged 18 and older.
- Massive PE (confirmed by CTPA).
- Signs of RV overload/dysfunction (at least one)³ associated with persistent hypotension or shock⁴.

³

- RV end-diastolic diameter more than 30 mm (parasternal long axis);
- RV/LV end-diastolic diameters ratio more than 0.9;
- hypokinesis of RV-free wall (Mc Connel sign);
- tricuspid regurgitant jet velocity in systole more than 2.6 m/s [1, 2].

⁴

- cardiac arrest;
- obstructive shock (systolic BP <90 mmHg or vasopressors required to achieve a BP \geq 90 mmHg despite an adequate filling status, in combination with end-organ hypoperfusion);
- persistent hypotension (systolic BP <90 mmHg or a systolic BP drop \geq 40 mmHg for >15 min, not caused by new-onset arrhythmia, hypovolaemia, or sepsis) [1, 2].

- Patient consent to use reliable contraceptive methods throughout the study and for 3 weeks after:
 - women who have a negative pregnancy test and use the following contraceptives: intrauterine devices, oral contraceptives, contraceptive patch, long-acting injectable contraceptives, double barrier method of contraception. Women who are not capable of bearing children (documented conditions: hysterectomy, tubal ligation, infertility, menopause for more than 1 year) can also take part in the study;
 - men using barrier contraceptives. The study may also include men who are not capable of bearing children (documented conditions: vasectomy, infertility).
- Signed and dated informed consent from the patient to participate in the trial.

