7.2. Exclusion criteria

- Increased risk of bleeding:
 - extensive bleeding at present or within the previous 6 months, hemorrhagic diathesis;
 - intracranial (including subarachnoid) hemorrhage at present or in history, suspicion of a hemorrhagic stroke;
 - hemorrhagic stroke or unknown etiology stroke in anamnesis;
 - ischemic stroke or transient ischemic attack within the last 6 months, with the exception of the current acute ischemic stroke within 4.5 hours;
 - central nervous system diseases in anamnesis (including neoplasms, aneurysm, surgery on the brain or spinal cord);
 - major surgery or major trauma within the previous 3 months, recent traumatic brain injury;
 - prolonged or traumatic cardiopulmonary resuscitation (> 2 min), labor within the previous 10 days, recent puncture of an uncompressible blood vessel (eg, subclavian or jugular vein);
 - severe liver disease, including liver failure, cirrhosis, portal hypertension (including esophageal varices) and active hepatitis;

- confirmed peptic ulcer of the stomach or duodenum within the last three months;
- a neoplasm with an increased risk of bleeding;
- simultaneous treatment with oral anticoagulants, for example, warfarin with INR>1.3;
- arterial aneurysms, defects in the development of arteries / veins;
- severe uncontrolled arterial hypertension;
- acute pancreatitis;
- bacterial endocarditis, pericarditis;
- suspicion of a dissecting aortic aneurysm;
- any other conditions, in the opinion of the doctor, associated with a high risk of bleeding.

- Lactation, pregnancy
- Known hypersensitivity to Actilyse®, Fortelyzin®.

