10. THERAPY DURING THE TRIAL

Study drug: Fortelyzin®

Manufacturer: «SuperGene», LLC, Russia

Drug description

Pharmaceutical form: lyophilizate for preparation of a solution for intravenous administration, supplied with a solvent

Detailed description:

Lyophilizate: tablet-like freeze-dried mass of white or almost white color.

Solvent: colorless transparent liquid.

Reconstituted solution: colorless, transparent or slightly opalescent liquid.

Composition:

Active substance: Forteplase® (recombinant protein containing the amino acid sequence of staphylokinase) 5 mg (745 000 IU).

Excipients: L-arginine – 15,0 mg, L-histidine – 2,0 mg, glycine – 30,0 mg, povidone-17 – 20,0 mg, polysorbate-20 – 0,4 mg.

Solvent: 5mL ampule of sodium chloride 0.9% solution for injection

Dosage regimen: Fortelyzin® will be assigned at a dose of 15 mg (2 235 000 IU).

Route of administration: intravenously in the form of a single bolus injection for 10-15 sec. The solution of Fortelyzin® is prepared immediately before administration: the content of a 5 mg vial (745 000 IU) is diluted in 5 ml of 0.9% sodium chloride solution. Non-storable!

Labeling: «Product for clinical trial only».

Active Comparator: Actilyse®**Manufacturer:** Boehringer Ingelheim Pharma GmbH & Co. KG**Drug description****Pharmaceutical form:** lyophilizate for preparation of a solution for infusion supplied with a solvent.**Detailed description:**

Lyophilizate: freeze-dried mass of white or light yellow color.

Solvent: colorless transparent liquid

Composition:

Active substance: Alteplase 50,0 mg

Excipients: L-arginine: 1742 mg,

Phosphoric acid, 85 %: up to pH 7,2 ± 0,2,

Polysorbate 80: 3,5-5,0 mg.

The excess is 3,5 % of the nominal amount of the active ingredient and excipients in the vial.

Residual traces: gentamicin (used in the production process).

Each vial of solvent contains:

Water for injection: 50 ml

1 ml of the solution after dilution contains 1 mg of alteplase.

Dosage regimen:

Actilyse® is administered in accordance with the instructions for use in ischemic stroke at a dose 100 mg.

Labeling: «Product for clinical trial only».

Previous treatment

Every effort should be made to find out what treatment the patient received within 30 days before administration of the study drug. The names of the drugs, the start and end dates of their use should be registered in the CRF.

Permitted concomitant therapy

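### Section 10 doses the Actilyse control arm by the ischemic stroke instructions; the printed 100 mg is the PE dose, so the indication must be corrected and the schedule stated

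*Combined protocol and SAP*

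**What the plan says.** Section 10, under the active comparator's dosage regimen, states that Actilyse "is administered in accordance with the instructions for use in ischemic stroke at a dose 100 mg". The aim (Section 5), the population (Section 7) and the official title all concern massive PE.

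Alteplase doses appear in four other places:

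- Section 1, on the earlier stroke trial, describes the comparator as a "bolus infusion at a dose of 0.9 mg/kg (maximum 90 mg) for patients with acute ischemic stroke within 4.5 hours" of onset.
- Section 2 says the Actilyse dose "is 100 mg for STEMI patients and 90 mg for patients with ischemic stroke".
- Section 1, in the dose rationale for massive PE, says of Actilyse: "It used at a dose of 100 mg, the same as for STEMI".
- Section 1, in the list of guideline thrombolytics for massive PE, gives "alteplase according to the standard scheme of 100 mg for 2 hours".

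The protocol summary (trial design) and Section 8 say only that Actilyse follows its instruction for use, with no indication, dose or schedule. The title and aim call the control a bolus infusion, without a split. For Fortelyzin, Section 10 gives the dose (15 mg), the route and the injection time (10-15 seconds). For Actilyse it gives a total dose and the stroke reference.

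**The concern.** This sentence is the operative dosing rule for the control arm. It points sites to instructions for a disease the trial does not study, and it pairs that reference with a dose that the protocol's own stroke figures cannot produce. A reader who takes it literally cannot satisfy both halves.

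The printed number settles the total dose but not how to give it. Section 10 leaves bolus, rate and duration to the cited instructions, and the only indication cited is the wrong one.

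The drug is a thrombolytic given to patients with shock or persistent hypotension, and the rule covers the whole control arm of an open-label non-inferiority trial with death as the primary outcome. The comparator regimen in such a trial should be readable in one way only.

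**Working it through.** **1. Does the printed dose match the trial's indication?** Printed dose (Section 10): 100 mg. PE dose (Section 1, guideline list and dose rationale): 100 mg. Difference: 100 − 100 = 0 mg. The number fits massive PE.

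**2. Does the printed dose match the cited indication?** The stroke rule quoted in Section 1 is dose = min(0.9 mg/kg × weight, 90 mg). The ceiling is reached at 90 / 0.9 = 100 kg, so the largest possible dose is 90 mg. Section 2 also gives 90 mg for stroke. The smallest gap is 100 − 90 = 10 mg, and 10 / 100 = 10% of the printed dose.

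Below 100 kg the gap widens. The protocol gives no weight distribution, so these weights are assumptions:

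| Assumed weight | Dose under the stroke rule | Gap from 100 mg |
|---|---|---|
| 60 kg | 0.9 × 60 = 54 mg | 46 mg |
| 70 kg | 0.9 × 70 = 63 mg | 37 mg |
| 80 kg | 0.9 × 80 = 72 mg | 28 mg |
| 100 kg or more | 90 mg | 10 mg |

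These figures measure the conflict inside the sentence. They are not doses that anyone is shown to receive.

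**3. Which half is wrong?** Step 1 gives exact agreement with PE and step 2 gives disagreement with stroke at every weight. The indication is therefore the error, not the number.

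**4. Is a schedule prescribed?** Setting the texts side by side:

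- Section 10 has no Actilyse duration, rate or bolus amount.
- The summary and Section 8 defer to the instruction for use.
- The title and aim say bolus infusion but give no split.
- The only duration, 2 hours, is in the Section 1 guideline list, and it is not carried into Section 10 as the trial regimen.

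**5. What would the PE regimen look like in practice?** Section 10 says "1 ml of the solution after dilution contains 1 mg of alteplase", with 50 mg per vial. So 100 mg is 100 / 50 = 2 vials and 100 mL. Over 2 hours the mean rate is 100 / 2 = 50 mL per hour, before any bolus split.

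**6. Is the sample size touched?** Section 17's formula with 10% mortality in both arms, a 10-point margin, one-sided 2.5% and 80% power gives (1.960 + 0.842)² × (0.09 + 0.09) / 0.10² = 7.849 × 0.18 / 0.01 = 141.3. This agrees with the stated 141 (142 if rounded up). Dose is not an input.

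**7. Reach of the sentence.** It governs 155 of 310 planned patients, or 50%.

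**The case against.** The strongest reply is that the operative number is right. A site that gives 100 mg gives the PE dose, and clinicians treating massive PE are unlikely to reach for a stroke regimen. This stands, and it limits the point to a wrong reference beside a correct total dose.

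Second, dosing a marketed comparator by its instructions for use is legitimate incorporation by reference, and the 2-hour scheme is in the document. Section 1 takes it from the two guidelines cited as references 1 and 2, and Section 10 cites the same two for patients' treatment. This stands in part. A reader might infer that the protocol contains no Actilyse schedule at all, and that would be wrong. But the guideline sentence in Section 10 sits under permitted concomitant therapy and names no alteplase schedule. Incorporation by reference also works only if the reference is to the right indication.

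Third, the stroke figures in Sections 1 and 2 describe another trial and general pharmacology; they are not rival dosing rules for these patients. Agreed. They are used here only to show that stroke and 100 mg do not belong together.

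Fourth, the text looks translated (stray Russian words remain in Sections 12 and 18), so the wording held at sites may be correct. That is possible and cannot be settled from this document. The printed version needs correcting either way.

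A reader might also be tempted by two further inferences. One is that monitors have no dose to check, or that patients could be withdrawn for a protocol violation. The documents do not support this: 100 mg is printed, it agrees with Section 1, and nothing suggests that giving it would count as a violation. The other is that the stroke reference has a purpose, because Section 7.2 excludes recent stroke "with the exception of the current acute ischemic stroke within 4.5 hours". That is an eligibility exception and says nothing about dosing.

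**Conclusion.** The point holds as an error of indication in the control-arm dosing line, with the administration schedule missing from Section 10 itself. The conflict inside the sentence is at least 10 mg (10% of the printed dose). The discrepancy between the printed dose and the protocol's PE dose is 0 mg.

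It might be inferred that control patients are underdosed, that they are infused on a different schedule, or that a weakened comparator undermines the 10-point margin. None of this is shown. A lower dose would arise only if a site set aside the printed number, and nothing indicates that any would. The stroke infusion schedule is not in the documents, so a schedule difference cannot be demonstrated. Sample size, margin, endpoints and analysis are unaffected.

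The conclusion assumes that the printed English text reflects the rule in force. Severity: a simple required correction, justified by where the error sits and how little it costs to remove, not by demonstrated harm.

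**What to change.** - In Section 10, replace the reference to ischemic stroke with pulmonary embolism.
- State the regimen there: 100 mg (two 50 mg vials, 100 mL) over 2 hours, with any bolus and infusion split taken from the PE instructions and confirmed by the sponsor. The split has to come from that source because this document does not give it.
- Make the protocol summary and Section 8 refer to that text.
- Check the source-language wording and notify any active sites.
- If control patients have already been treated, list any Actilyse dose other than 100 mg from the drug register that Section 14 already requires.

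The cost is a short amendment to one dosing paragraph, two cross-references and a site notice, plus one register check if dosing has begun. Nothing in the sample size, endpoints or analysis changes.

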11. EFFICACY ENDPOINTS

- Primary efficacy outcome – death from any causes within 7 days;
- Secondary efficacy outcome – PASP (V1, V2, V4, V5);
- Secondary efficacy outcome – hemodynamic collapse within 7 days;
- Secondary efficacy outcome – recurrent PE within 7 days;
- Secondary efficacy outcome – death from PE within 7 days;
- Secondary efficacy outcome – death from any causes within 30 days;
- Secondary efficacy outcome – clinical composite of hemodynamic collapse within 7 days + recurrent PE within 7 days + death from any causes within 30 days.

12. SAFETY ENDPOINTS

- Safety outcomes – ischemic and hemorrhagic strokes within 7 days;
- Safety outcomes – bleedings BARC type 3 and 5;
- number and severity of SAEs and AEs in organs and systems.

Adverse events

Adverse event (AE) is an unfavorable medical occurrence in a patient administered a pharmaceutical product, which may not have a causal relationship with its use. Thus, an AE can be any adverse symptom (including deviation of the laboratory value from the norm), a complaint, or a disease, the time of occurrence of which does not exclude a causal relationship with the use of the medicinal product, regardless of the presence or absence of such communication.

Information about AEs should be collected at each visit by interviewing the patient, as well as during physical examination and evaluation of laboratory and instrumental data. All AEs that occur during the trial should be evaluated and documented.

When registering an adverse event, the following information should be reflected, if possible:

- the exact time of AE occurrence и разрешения

- the nature of the AE
- severity (mild, moderate, severe)
- causal relationship with the study drug
- whether the AE is serious
- actions taken (whether AE required any therapeutic measures)
- outcome

AEs Grading:

- **Mild:** the presence of signs or symptoms that do not affect daily activities.
- **Moderate:** AE has sufficient intensity to interfere with daily activities.
- **Severe:** inability to work or perform daily activities.

The connection between the development of AE and the use of the study drug is determined by the WHO scale:

- ***definitely related:*** Clinical manifestations of AE, laboratory findings deviations that occur during the period of drug administration, cannot be explained by the presence of existing diseases and the influence of other factors. Manifestations of AE regress after the drug discontinuation and occur again after repeated administration.
- ***Probable.*** Clinical manifestations of AE, laboratory findings deviations are associated with the time of drug administration, unlikely to be related to concomitant diseases or other factors, and which regress with drug withdrawal. Response to the drug re-challenge is unknown.
- ***Possible.*** Clinical manifestations of AE, laboratory findings deviations associated with the time of drug administration, but they can be explained by the presence of concomitant diseases or other drug administration and the influence of chemical compounds. Information on drug withdrawal response is unclear.
- ***Questionable.*** Clinical manifestations of AE, changes in laboratory findings occur in the absence of a clear temporal association with the product administration;

other factors are present (medicinal products, diseases, chemicals), which may be the cause of their occurrence.

- ***Unlikely.*** Clinical manifestations of AE, laboratory findings deviations related to UAR, are difficult to assess. Additional data are needed for assessment, or the data are currently being analyzed.
- ***Unclassified.*** Reports on suspected AE cannot be assessed, due to insufficient information, or it is contradictory.

In the case of AEs, the choice of measures (follow-up, non-drug or drug therapy, hospitalization, and/or prolongation of existing hospitalization) is made by the physician-investigator based on the patient's interests to create optimal conditions and provide the patient with needed medical care.

Patients are monitored in the center until the full completion of any AE that occurred during the trial, and in the case of the development of a chronic disease – until the condition is stabilized. AEs in the form of changes in laboratory findings are observed until the normalization of the values or until the diagnosis of the chronic disease that caused such changes.

Serious adverse event (SAE)

A serious adverse event (SAE) is defined as any adverse event (AE) that at any dose results in:

- * death and/or disability;
- * development of a life-threatening condition;
- * prolongation of existing hospitalization;
- * development of congenital anomalies or malignant tumors.

In addition, any severe bleedings will be considered as SAEs in this trial:

- major bleeding (type 3 and 5) according to BARC classification;
- hemodynamic collapse within 7 days.

AEs that do not fall into these categories should not be regarded as serious.

Any SAE, regardless of the causal relationship with the drug under trial, must be reported to the Ministry of Health of the Russian Federation no later than 24 hours after the Investigator became aware of the SAE.

All paragraphs in the appropriate SAE report form must be filled in. Information about the SAE should be included in the CRF.

Bleedings

All bleedings should be registered in the patient's CRF. Each bleeding is classified according to BARC. Bleeding that is classified according to BARC as type 3 or 5 are considered as SAE in this trial.

Safety assessment is carried out based on the number and severity of AEs and SAEs detected during the trial.

If a serious adverse event occurs, the Investigator must:

- provide (if necessary) appropriate qualified medical care, including laboratory and instrumental studies;
- inform to the Sponsor within 24 hours about the occurrence of SAE and send (fax, e-mail) a Report form on a SAE;
- indicate all adverse events in the patient's CRF;
- continue to monitor the patient's condition until the SAE is fully completed.

In connection with SAE occurrence, the sponsor is obliged to:

- notification of administrative control authorities;
- suspend or cancel the clinical trial.

Contact information for security specialists is listed below:

Company name – Sponsor	The Russian Academy of Sciences
Legal address	[name]
Actual address	[name]
Phone [contact]
e-mail	[contact]
Authorized representative of the Sponsor	[name] [contact]

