8. DESIGN AND PLAN OF RESEARCH ACTIVITIES

This trial is a multicenter, open-label, randomized, parallel-group, phase III b non-inferiority trial to compare the efficacy and safety of the trial drug.

The trial will include 310 patients with massive PE. The patients will be monitored for 30 days: 1-2 days in the Intensive Care Unit and the Department of cardiology in the remaining days before discharge (on average 14 days), with an outpatient visit on the 30th day.

Start of research, initiation of centers: «_____» 20____

Enrollment of patients: «_____» 20____

Result processing and reporting: «_____» 20____

The enrollment period may be extended to total patient enrollment if a research center fails to enroll the planned number of patients. The end date of the trial is considered to be the end date of the trial in all patients involved.

In each research center, the subject of the trial is assigned a serial number that corresponds to the sequence of patient inclusion in the trial. The serial number is reflected in the CRF. The list of patient's identification is stored in the trial file. Patients are included in the trial only after signing the Informed consent form.

Before the trial, all patients will undergo the following procedures: collection of thorough medical history, signs of hemodynamic collapse, risk stratification to assess the prognosis according to the PESI classification, a physical examination, CTPA, ECG, EchoCG with the definition of PASP, ultrasound diagnostics of the inferior vena cava will be performed; blood and urine samples will be taken for laboratory tests:

- **complete blood count:** hemoglobin, red blood cells, hematocrit, leukocyte formula: neutrophils, eosinophils, basophils, monocytes, lymphocytes, platelets, ESR;
- **biochemical blood parameters:** total protein, creatinine, urea, AST, ALT, CK, NT-proBNP, total bilirubin, glucose, sodium, potassium, total cholesterol, HDL-cholesterol, triglycerides;

- **coagulogram:** fibrinogen, aPTT, INR, prothrombin, D-dimer.
- **general urine analysis:** red blood cells.

After enrollment, patients will be randomized using the «envelope method» into two equal groups of 155 patients each (a total of 310 people, including 10% who may have dropped out) and assigned to receive either Fortelyzin® or Actilyse®. Fortelyzin® will be given as single i.v. bolus over 10-15 seconds. Actilyse® will be administered following the instruction for use.

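### The closed SAE list omits new hospitalisation, so a readmission between discharge and day 30 that meets no other listed criterion is classed as non-serious

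*Combined protocol and SAP*

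**What the plan says.** Section 12 (Serious adverse event) gives four general criteria: "death and/or disability", "development of a life-threatening condition", "prolongation of existing hospitalization" and "development of congenital anomalies or malignant tumors". It adds two trial-specific ones: "major bleeding (type 3 and 5) according to BARC classification", with no time limit, and hemodynamic collapse within 7 days. The next sentence closes the list: "AEs that do not fall into these categories should not be regarded as serious". New hospitalisation is not a criterion, there is no category for other medically important events, and no other section adds either.

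Seriousness has two uses in the plan. One safety outcome in Section 12 is the "number and severity of SAEs and AEs in organs and systems". SAE status also starts two 24-hour clocks, one for the report to the Ministry of Health and one for the report to the sponsor.

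Section 8 has patients in hospital "before discharge (on average 14 days), with an outpatient visit on the 30th day". AE and SAE registration is scheduled at that last visit, both in Table 5 and in Section 9.

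**The concern.** Part of the planned follow-up is spent out of hospital. In that part no stay exists to be prolonged, so the only hospitalisation criterion cannot be met by the admission itself. The closing sentence stops the investigator from using judgement to fill the gap. An event that sends a patient back to hospital is then graded lower than the same event occurring a few days earlier on the ward, and seriousness comes to depend partly on the date of discharge.

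At stake are the completeness of a named safety outcome after discharge and the speed at which such events reach the sponsor and the Ministry. The primary endpoint, the sample size and the non-inferiority comparison are not affected.

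**Working it through.** The plan states no figure to reproduce. The check is a reading of the definition against the follow-up schedule, plus one subtraction.

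**1. Could the prolongation criterion be read to include a new admission?** No. Earlier in Section 12, the paragraph on managing AEs names hospitalisation and the prolongation of a stay as two separate measures. The protocol treats them as different things, expects an AE to lead to either, and carries only the second into the SAE definition.

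**2. Do other criteria catch readmissions?** Some do. Applying the list as written to an event at, say, day 20 that leads to admission:

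- Fatal, disabling or life-threatening event: SAE.
- BARC type 3 or 5 bleed: SAE at any time.
- Recurrent PE or other thrombosis judged neither life-threatening nor disabling: AE only.
- Bleed below BARC type 3: AE only.
- A further AE that lengthens the readmission: that AE can qualify through prolongation, but the event that caused the admission does not.

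The third and fourth kinds of event would be SAEs if they occurred before discharge and lengthened the stay.

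**3. Do other endpoints cover the gap?** Only in part. Sections 11 and 12 count recurrent PE, hemodynamic collapse and stroke within 7 days only. Death is counted to day 30, and BARC type 3 and 5 bleeding has no stated limit. After day 7, any other non-fatal clinical event appears only in the AE and SAE tallies.

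**4. How long is the exposed window?** Inputs from Section 8: follow-up of 30 days, an average of 14 days before discharge, and 1–2 days in intensive care.

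- If the 14 days are the whole stay: 30 − 14 = 16 days, and 16/30 = 53%.
- If the 14 days are the cardiology stay after intensive care, discharge falls at day 14 + 1 = 15 to 14 + 2 = 16. The window is 30 − 15 = 15 days (15/30 = 50%) to 30 − 16 = 14 days (14/30 = 47%).

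The window is thus 14 to 16 of 30 days, depending on how the 14 days are read. It is a share of calendar time for an average patient.

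**The case against.** The strongest reply is that the gap is narrow and nothing disappears.

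- **Scope.** A reader might infer that every readmission after discharge becomes non-serious. The list does not support that, as step 2 of the working shows. In patients enrolled with massive PE and shock or persistent hypotension, many recurrent emboli or strokes needing admission would qualify as life-threatening or disabling. This stands, and it limits the point to the milder events.
- **Size.** A reader might take 47–53% as the share of SAEs missed. It is not. Risk is unlikely to be even over 30 days after a single bolus with a 30-minute terminal half-life (Section 2), and the documents give no readmission rate. This stands.
- **Recording.** Every AE is documented with its severity, the action taken and the outcome, and the safety outcome covers AEs as well as SAEs. A readmission therefore moves from one count to the other and could be recovered from the CRF. This stands for the record, but it does not repair the SAE count as defined or the lost deadline.
- **Reporting.** Section 4.2 says the authorities will be told of all AEs associated or possibly related to the study drug. That softens the consequence for related events, but it sets no 24-hour limit. Section 12 requires SAE reporting regardless of causality, so it does not replace that duty.
- **Bias.** The trial is open-label and discharge is decided by staff who know the treatment, so a reader might infer that the SAE comparison favours one arm. The same rule applies to both arms, and the documents show no difference in discharge practice or readmission. That inference is not supported.

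**Conclusion.** The point holds in its narrow form. Followed as written, Section 12 classes as non-serious any readmission between discharge and day 30 that meets no other listed criterion. That event is missing from the SAE count and carries no 24-hour report, while remaining in the AE record. This is a stated rule that gives the wrong classification, not a missing detail. The protocol's own separation of hospitalisation from prolongation suggests that a term was dropped.

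The exposed window is about 14 to 16 of 30 days, on the Section 8 average and either reading of it. The number of SAEs affected cannot be derived from the documents, and no direction of bias between arms is shown. The change should be made because it corrects a named safety outcome and expedited reporting at little cost. The primary analysis does not depend on it.

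**What to change.** In Section 12 and on the SAE form, add *requires hospitalisation* beside the existing criterion on prolongation. The closing sentence then no longer excludes readmissions and can stay; deleting it is not required, and keeping it preserves a clear boundary for what counts as serious.

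The direct cost is one line in each document and a few more SAE reports. There is one knock-on effect. Section 12 says that when an SAE occurs the sponsor is obliged to notify the authorities and to suspend or cancel the trial, whereas Section 7.5 ties early termination to SAEs that are associated with the trial drug and make its further use unacceptable. These two texts do not agree now, and a wider SAE list would bring the first into play more often. They must be reconciled with each other and with the amended definition.
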